## DATA ANALYTIC PLAN

**Clinical-trial data analyses.** Linear regression will be used for continuous outcomes with treatment condition and baseline values entered as covariates. We will separately model outcomes at 6 weeks and 12 weeks respectively. Participants with missing follow-up data will be included using multiple imputation to reduce bias in effect estimates. Within-condition changes will be modeled using linear regression with assessment and value at baseline as independent variables. For zero-inflated count outcomes, hurdle models will be used to compare treatment conditions on (1) the probability of having such encounters during the 12-week follow-up period (binary model, fit using modified Poisson regression to obtain aRR estimates) and the number of weeks with such encounters among those with one or more encounters (count model, fit using negative-binomial regression to obtain adjusted incidence rate ratio [aIRR] estimates), with offset terms for the natural logarithm of the number of weeks surveys were completed. Models will use a two-tailed alpha level of 0.05 to detect significant differences between Bolster and control, with patterns of effect sizes and 95% confidence intervals (CIs) examined for all outcomes to inform future trials. As this is a pilot trial, conclusions will involve interpretations of overall effect sizes.

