## OVERVIEW

**Study Objectives.** Caregivers play a critical role in the recovery of young adults with early psychosis. The involvement of a supportive caregiver is associated with more rapid and sustained treatment engagement, reduced relapse risk, and improved functional outcomes. Family-focused interventions reduce caregiver burden and reduce risk of patient relapse, but many caregivers face barriers to access. mHealth interventions have shown promise in providing self-guided interventions to individuals that face barriers to services. Our team conducted a multi-phase user-centered design and development process to build Bolster, an mHealth intervention for caregivers to young people experiencing early psychosis. Bolster is designed to provide psychoeducation, communication coaching, and self-care support consistent with principles of family psychoeducation, cognitive behavior therapy, and motivational enhancement. The objective of this project is to evaluate the acceptability and preliminary effectiveness of Bolster, as well as examine the feasibility of our proposed study methods should results warrant future testing in a fully-powered trial. Participants will be sixty (N = 60) caregivers randomized (2:1) to either receive a collection of resources on psychosis and caregiving from scientific and advocacy organizations (control arm) or the same resources and the Bolster app (active intervention or Bolster arm). Participants will complete assessments of outcomes at baseline as well as 6- and 12-weeks after beginning the intervention. This study aims to evaluate whether Bolster improves caregiver knowledge and illness appraisals, reduces distress, improves coping, family communication, and results in increased treatment facilitation and treatment received by the affected young adult.

**Design.** This is a parallel group randomized controlled trial design. Participants are randomized 2:1 to receive either Bolster (Bolster arm) or control exemplar resources gathered from multiple scientific and advocacy organizations. Randomization is stratified based on whether the identified patient had engaged in specialty mental health within the past year. Primary outcome assessments are collected remotely with electronic data capture at (1) baseline, (2) 6 weeks after app installation, and (3) 12 weeks after app installation. Treatment engagement outcomes are reported remotely weekly during the study period.

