**Recruitment.** Participants are recruited through online study ads (i.e. Google, Instagram, and YouTube) as well as distribution through mental health advocacy organization and treatment websites and listservs. All screeners and study questionnaires are completed through online data capture (i.e. REDCap). Once participants click a link to the study landing page from a recruitment ad or posting, they are required to demonstrate understanding of study details through a comprehension questionnaire, provide informed consent and are subject to a series of steps to ensure eligibility for the study and identity verification. Study team members evaluate screening data and conduct confirmatory synchronous screening by phone. The invitation to complete the baseline assessment is sent to participants after eligibility confirmation via text message. After

baseline is complete, participants are invited to asked to complete an installation session wherein they are introduced to their intervention, and oriented to study details. Participants are randomized to condition (via a pre-set stratified randomization algorithm, see above) at the time of the installation session. Once participants have installed and been oriented to either the study app and online resources or online resources only, members of the study team are available to answer questions about study interventions or respond to concerns about the study. Up to three times during the study period, participants in the Bolster arm receive outreach via text message and phone call if they stopped using the app for five consecutive days (confirmed via app usage logs). This outreach assesses for technical issues or concerns from participants about app use. To match this outreach in the Bolster arm, all participants in the control arm receive two phone calls during their time in the study, once in the third week and once in the ninth week. Subsequent assessments are sent to participants via text messages 6 and 12 weeks after their installation session. Participants are compensated with \$60 gift cards for completing each assessment battery (or, in the case of baseline, baseline and installation session both).

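### The 6- and 12-week linear models leave out the randomisation stratum; adding it could narrow the 95% CIs slightly, depending on how allocation is done within strata and how prognostic the stratum is (minor, cheap to fix)

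*Combined protocol and SAP*

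**What the plan says.** The Design paragraph of the Overview states that "Randomization is stratified based on whether the identified patient had engaged in specialty mental health within the past year". The Recruitment paragraph of the Methods says that participants are assigned "via a pre-set stratified randomization algorithm, see above". Neither place says whether allocation within a stratum is blocked, otherwise balanced, or simple.

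For the analysis, the Data Analytic Plan states: "Linear regression will be used for continuous outcomes with treatment condition and baseline values entered as covariates". It adds "We will separately model outcomes at 6 weeks and 12 weeks respectively", and on dropout "Participants with missing follow-up data will be included using multiple imputation to reduce bias in effect estimates". The stratum appears in none of the models described there, and no reason for leaving it out is given. The phrase on baseline values most naturally means each outcome's own baseline score.

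The output that matters is also stated: "patterns of effect sizes and 95% confidence intervals (CIs) examined for all outcomes to inform future trials".

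**The concern.** A trial that stratifies its randomisation usually carries the stratum into the analysis, for two reasons. First, if the stratum predicts the outcome, leaving it out keeps explainable variation in the error term. Second, balancing the arms within strata reduces the true variability of the treatment estimate. A model that ignores the stratum does not register that reduction, so its standard error is too large.

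At stake is the width of the confidence intervals in a 60-person pilot whose stated product is effect sizes and intervals for planning later trials. The validity of the treatment comparison is not at stake.

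**Working it through.** **No figure to reproduce.** The plan gives no power calculation, SD, dropout rate or expected effect, so the check asks how much CI width depends on the stratum.

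**Inputs from the documents.** N = 60; 2:1 allocation, so 40 and 20; two-sided alpha 0.05; a linear model with arm and baseline score (residual df = 60 − 3 = 57), or with the stratum added (df = 56).

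**Assumed inputs.** Baseline–outcome correlation 0.5; 40% of participants in one stratum; R² = share of residual variance, after the baseline score, that the stratum explains, taken over a range; allocation either in blocks of 3 within strata or simple.

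**Blocked allocation.** Arm and stratum are nearly uncorrelated, so

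width without ÷ width with = [1/√(1 − R²)] × t(0.975, 57)/t(0.975, 56) = [1/√(1 − R²)] × 2.0025/2.0032.

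- R² = 0.02: 1.0098, about 1.0% extra
- R² = 0.05: 1.0256, about 2.6% extra
- R² = 0.10: 1.0537, about 5.4% extra

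The model's standard error is then too large by about 1/√(1 − R²), so the effective critical value at R² = 0.10 is 2.0025/√0.90 = 2.111. On 57 df that is a two-sided level of 3.9%; simulation gives about 3.8%.

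**Simple allocation.** Arm and stratum now correlate by chance, with expected squared correlation about 1/(N − 1) = 1/59 = 1.7%. Adjusting for the stratum pays for that overlap:

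width without ÷ width with ≈ √[(1 − 1/59)/(1 − R²)] × 2.0025/2.0032.

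- R² = 0: 0.991, so adding the stratum widens the CI by 0.9%
- R² = 0.01: 0.996, so adding it widens the CI by about 0.4%
- R² = 0.02: 1.001, about 0.1% extra without it
- R² = 0.05: 1.017, about 1.7% extra without it
- R² = 0.10: 1.045, about 4.5% extra without it

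Break-even is where 1 − R² = (58/59) × (2.0025/2.0032)², that is R² ≈ 1.8%, or about 2%.

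**Simulation.** Trials under no treatment effect, with stratum sizes left random:

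| R² | Extra width without stratum, blocks of 3 | Type I error without it, blocks of 3 | Extra width without stratum, simple |
|---|---|---|---|
| 2% | 1.0% | 4.6–5.0% | 0.1% |
| 5% | 2.6% | 4.2–4.4% | 1.5–1.6% |
| 10% | 5.4% | 3.7–3.8% | 4.4–4.5% |

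Under simple allocation, type I error without the stratum stays near 5% (4.7–5.2%). In outcome SD units with blocking, the CI half-width without and with the stratum is 0.477 and 0.472 at 2%, 0.478 and 0.466 at 5%, and 0.478 and 0.453 at 10%.

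**With missing data.** Assuming 15% of outcomes missing at random and multiple imputation, the extra width at 2, 5 and 10% is 0.8%, 2.3% and 5.2% (blocks of 3), or about 0, 1.5% and 4.2% (simple).

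**The case against.** The strongest case against is that nothing in the documents shows the stratum to be prognostic. It records the patient's service use, while most continuous outcomes are caregiver self-reports, each already adjusted for its own baseline. The treatment-facilitation scale (MASS-CG) is the likeliest exception, and it too is baseline-adjusted. Eligibility narrows the contrast further: the patient must have been out of specialty services for at least three months, so the strata mainly separate engagement roughly 3 to 12 months ago from earlier or none. At 5% of residual variance or less the gain would hardly change planning. In simulation, chance alone varies the CI width between trials by about 9–11% (coefficient of variation), several times the 1–2.6% gain under blocking at 2–5%. All of this stands. It limits the point to a low-priority improvement, but does not remove it, because the cost is also very small.

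A reader might infer more than the documents support in four ways:

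- **That any prognostic stratum makes the planned CIs too wide.** Under simple allocation this fails below about 2% of residual variance, where adding the stratum widens the CI slightly.
- **That the planned test is conservative.** This needs balance within strata, and the documents do not say how allocation is done.
- **That the omission causes bias or extra false positives.** It causes neither.
- **That the binary engagement model ("binary model, fit using modified Poisson regression to obtain aRR estimates") needs the same change.** No precision gain was shown there. Omitting the stratum produced no excess in the standard error under simple allocation, nor when engagement in the two strata was 40/40% or 50/30%. With the stratum included, the robust standard error ran about 2–8% below the true SD.

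**Conclusion.** The omission is in the text, and its consequence is conditional and small. With allocation balanced within strata, a prognostic stratum makes the planned intervals about 1% to 5.4% too wide over 2–10% of residual variance, with the test mildly conservative. With simple allocation the test is sound, and there is something to gain only above about 2%. The estimate is unbiased in both cases.

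These sizes rest on an assumed baseline correlation, stratum split and allocation method, and on an assumed range for prognostic strength; none of these is in the documents. The point is limited to the linear models for continuous outcomes and is minor.

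**What to change.** Replace the covariate sentence in the Data Analytic Plan with wording such as:

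> Each continuous outcome will be analysed by linear regression on treatment condition, the outcome's own baseline value and the randomisation stratum (past-year specialty mental health engagement, yes/no); the imputation model for these outcomes will include the same variables.

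The cost is one sentence and one degree of freedom (57 to 56). No new data are needed, since the stratum is known at randomisation. If the stratum turns out not to be prognostic, the CI is about 0.1% wider with blocked allocation and 0.9% wider with simple allocation (0.2% and 1.2% under the 15% missing-data assumption). No change to the hurdle models is requested under this point.

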## METHODS

**Participants.** Participants are 60 individuals (1) aged 18 years or older, who (2) live in the United States, and (3) identify as a caregivers to a youth or young adult experiencing early psychosis, wherein this is defined as (3a) being between the ages of 15 and 35, who (3b) within the last five years started experiencing symptoms meeting the following criteria: (3c) A positive screen according to the Caregiver Prime Screen - Revised (endorsed two or more responses of five or six ("somewhat"/"definitely" agree), as well as (3d) "hallmark symptoms" including (3d.1) the presence of psychotic symptoms represented by one or more of hallucinations, delusions, marked thought disorder, psychomotor disorder or bizarre behavior, as well as (3d.2) definite change of personality or behavior manifesting as two or more of the following: serious deterioration of function, marked social withdrawal, persistent self-neglect, episodic marked anxiety. The affected person must also be (4) not enrolled in specialty mental health services (i.e. a program wherein the affected person can access both psychiatry and counseling/therapy services) and has not been enrolled in such services for at least three months prior to screening. If an affected person is receiving one of these services, the caregiver reports that this is an inadequate level of care. Participants are also required to (5) own an Apple iPhone. Participants are excluded if they or their loved one is (1) incarcerated or living in a long-term care setting, (2) they failed to demonstrate understanding of study details in comprehension screening, or (3) the loved one is not enrolled in services only because they previously completed or "graduated" from a specialty treatment program for psychosis.

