Report of Treatment Engagement, Medication Provider	Change in Treatment Engagement, Medication Provider	Treatment facilitation / duration of untreated psychosis will be assessed according to participants' report of appointments attended by their relative in the past during the treatment period. This first category includes meeting with a clinician providing psychiatric medications. At screening, participants report treatment engagement over the previous three months and during the study period, participants are asked to report on this weekly.	Baseline, 12 weeks
Report of Treatment Engagement, Therapy or Counseling	Change in Treatment Engagement, Therapy or Counseling	Treatment facilitation / duration of untreated psychosis will be assessed according to participants' report of appointments attended by their relative in the past during the treatment period. This first category includes meeting with a clinician providing mental health therapy or counseling. At screening, participants report treatment engagement over the previous three months and during the study period, participants are asked to report on this weekly.	Baseline, 12 weeks
Knowledge About Schizophrenia Test (KAST)	Change in Illness Knowledge, Factual Knowledge	This is assessed with the Knowledge About Schizophrenia (KAST), an 18-item multiple-choice assessment examining individuals' knowledge of the etiology, symptoms, and prognosis of schizophrenia. Total scores indicate the number of correct responses and thus range from 0 to 18.	Baseline, 6 weeks, 12 weeks
Illness Perception Questionnaire for Schizophrenia Relatives (IPQSR), Coherence	Change in Illness Knowledge, Caregiver Self-rated	Illness appraisals will be assessed with the Illness Perception Questionnaire for Schizophrenia Relatives (IPQSR), a self-report scale of caregivers' beliefs about the severity, prognosis, and responsiveness to treatment of mental illnesses. Each item is rated on a 5-point scale (1 = strongly disagree; 5 = strongly agree), and totals are scored by summing individual items. For the coherence total, we are totaling the 5 items related to the caregiver's report of how much they understand or know about their loved one's illness. Scores range from 5 to 25 with lower scores indicating better self-rated understanding or coherence.	Baseline, 6 weeks, 12 weeks

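### Weeks in treatment are tested only among relatives who attended at least once, and no estimate of the amount of treatment over all randomised participants is planned

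*Combined protocol and SAP*

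**What the plan says.** The Overview (Study Objectives) asks whether Bolster "results in increased treatment facilitation and treatment received by the affected young adult". Methods (Outcome Measures) lists two engagement outcomes, one for medication providers and one for therapy or counselling. On how they are collected it says: "At screening, participants report treatment engagement over the previous three months" and "during the study period, participants are asked to report on this weekly".

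The Data Analytic Plan uses hurdle models for zero-inflated counts. It does not name these outcomes, but its references to encounters and to weeks fit the two engagement reports and nothing else in the measures table. The models have two parts:

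- a modified Poisson model for having any encounter during the 12 weeks, giving an aRR;
- a negative-binomial model for "the number of weeks with such encounters among those with one or more encounters", giving an aIRR, "with offset terms for the natural logarithm of the number of weeks surveys were completed".

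The test rule is general and does not exempt the second part: "Models will use a two-tailed alpha level of 0.05 to detect significant differences between Bolster and control". Effect sizes and 95% CIs are to be examined for all outcomes to inform later trials. No section plans a mean or rate of treatment weeks with zeros kept, or a combination of the two hurdle parts with a CI.

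**The concern.** Whether a relative attends at all during follow-up is known only after randomisation, and raising attendance is one of Bolster's purposes. The attenders in the two arms therefore need not be alike. If Bolster brings in relatives who would otherwise not have attended, they are in the Bolster subset and have no counterpart in the control subset. The aIRR then reflects that difference in mix as well as any effect on how long people attend.

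The design leaves room for such a mix. Relatives may already be using one kind of service at entry: "If an affected person is receiving one of these services, the caregiver reports that this is an inadequate level of care". Attenders can thus include continuing users and people who start partway through the 12 weeks. The offset counts weeks surveyed, not weeks since starting, so it does not correct for a late start.

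What is at stake is how the aIRR is read. Taken as the effect of Bolster on the amount of treatment, it could misinform the future trial that these effect sizes are meant to inform.

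**Working it through.** **Inputs from the document.** N = 60 randomised 2:1, so 40 Bolster and 20 control; 12 weeks of follow-up; two-sided alpha 0.05. The plan gives no attendance rate, mean number of weeks or sample-size calculation, so there is no figure of its own to reproduce.

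**Assumed inputs.** A share pc of controls attends (0.5 or 0.3), with a mean of 4 weeks. Bolster leaves those relatives unchanged and adds 20 percentage points of new starters who average s weeks. No surveys are missing and the ratios are unadjusted.

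**Formulas.**

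- Ratio for any encounter = (pc + 0.2) / pc
- Conditional ratio = [(4·pc + 0.2·s) / (pc + 0.2)] / 4
- All-randomised ratio = (4·pc + 0.2·s) / (4·pc)

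**Worked case, pc = 0.5 and s = 2.**

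- Any encounter: 0.7 / 0.5 = 1.40
- Conditional: (2.0 + 0.4) / 0.7 = 3.43 weeks; 3.43 / 4 = 0.86
- All randomised: 2.4 / 2.0 = 1.20
- Check: 1.40 × 0.857 = 1.20

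**Range over s.**

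| s (weeks) | Conditional, pc = 0.5 | All randomised, pc = 0.5 | Conditional, pc = 0.3 | All randomised, pc = 0.3 |
|---|---|---|---|---|
| 2 | 0.86 | 1.20 | 0.80 | 1.33 |
| 3 | 0.93 | 1.30 | 0.90 | 1.50 |
| 4 | 1.00 | 1.40 | 1.00 | 1.67 |
| 5 | 1.07 | 1.50 | 1.10 | 1.83 |

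At s = 4 the conditional ratio is 1.00 and the any-encounter ratio (1.40 or 1.67) equals the all-randomised ratio, so the planned aRR already carries the whole effect. The two part company only when s differs from 4, and the direction depends on whether s is lower or higher.

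**How visible this is at 40:20.** I simulated 20,000 trials per scenario. Weeks among attenders were 1 plus a beta-binomial count out of 11 (a + b = 4), and the log ratio of arm means was tested with a robust SE. For pc = 0.5:

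| s (weeks) | Conditional ratio below 1 | Significantly below 1 | aRR above 1 with conditional ratio below 1 | All-randomised ratio below 1 |
|---|---|---|---|---|
| 2 | 72% | 10% | 66% | 28% |
| 3 | 61% | 6% | 56% | 20% |
| 4 (no distortion) | 48% | 3% | 45% | 14% |

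The excess disagreement between the two parts that is due to conditioning is about 66 − 45 = 21 points at 2 weeks and 56 − 45 = 11 points at 3 weeks. The conditional ratio's 95% CI is about ×/÷ 1.6 (pc = 0.5) to 1.8 (pc = 0.3). That of the all-randomised ratio is about ×/÷ 2.0 to 2.6.

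**Covariate adjustment.** The plan does not list the hurdle covariates. I fitted a large-sample negative-binomial model for pc = 0.5, adjusted for one yes/no indicator of prior contact. If 60% of continuing attenders and 20% of the others had prior contact, the adjusted conditional ratio is 0.87 at s = 2 and 0.94 at s = 3. With 80% and 10% it is 0.90 and 0.95. Adjustment of this kind reduces the distortion without removing it. A richer baseline measure might do better.

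**The case against.** A hurdle model is a standard choice for counts with many zeros, and the plan states its conditioning openly. The binary part is a randomised comparison of any treatment against none, which is a natural measure where the outcome is framed around untreated psychosis. A point estimate of the amount can be rebuilt in simple cases by multiplying the aRR by the aIRR. The trial is a pilot that reports effect sizes with CIs. All of that stands, and it limits how much the point matters.

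The objection on noise also stands. Opposite-pointing parts arise in about 45% of simulated trials with no distortion, so most of the 66% or 56% is chance. The added ratio would rarely settle anything: with new starters at 2 weeks it is below 1 in 25% to 28% of trials and significantly above 1 in only about 7% to 8%.

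The objection does not supply a CI for the amount of treatment, and it does not make the aIRR a randomised contrast.

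A reader might go further and infer that the plan would miss a real increase in treatment, for example when the aIRR is 1.00 while treatment received rises by 40%. The documents do not support that: in that case the planned aRR is 1.40 and reports the full rise. Nor do they support a claim that the aIRR will be biased downwards. Nothing in them says how long new starters attend.

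**Conclusion.** The point holds in a limited form. The planned aIRR compares groups selected after randomisation and is tested as though it were an arm difference. It isolates an effect on duration only if those whom Bolster draws in resemble the other attenders, or if baseline covariates account for the difference. Otherwise it can differ in sign from the change in amount, as in the worked case of 0.86 against 1.20.

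That size rests wholly on assumed attendance rates and durations. Over the values tried, the conditional ratio runs from 0.80 to 1.10 while the all-randomised ratio runs from 1.20 to 1.83. With CIs as wide as those at N = 60, the consequence is mainly one of labelling and of which estimate is carried into the next trial. The gap concerns the amount of treatment only. The any-encounter comparison is sound as planned. I would class this as a change to consider.

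**What to change.** Keep both hurdle parts. For each engagement outcome:

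- Add the ratio of mean weeks with an encounter over all randomised participants, zeros included. Obtain it by combining the two hurdle parts or from one log-link count model on everyone, with a bootstrap or robust 95% CI. State that it serves estimation and not significance testing.
- Report the aIRR as descriptive and conditional on attendance, outside the 0.05 test.
- Handle missing weeks in one consistent way. Either impute missing weekly reports for everyone, so that all have 12 weeks and no offset is needed, or keep observed counts with the survey-weeks offset and report how many participants completed no survey, since log(0) excludes them.

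The cost is SAP wording and one extra model per outcome, on data already collected. The added ratio will have a wide CI (about ×/÷ 2.0 to 2.6) and will sometimes point the wrong way. In the simulations a simple robust interval covered slightly under 95% (about 93.5% to 94.6%). The aIRR would lose its standing as a tested effect.

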**Interventions.** Bolster is a self-guided iOS mobile app designed to provide self-guided support to caregivers to youth and young people experiencing early psychosis. It combines video, audio, and written text, and draws on principles of family psychoeducation, cognitive behavior therapy and motivational enhancement. Participants in both arms will be provided support resources from mental health advocacy organizations representing currently available resources for caregivers (including a selection from the National Alliance on Mental Illness and Mental Health America). They will also have access to the research team by phone for technical troubleshooting and support as necessary.

**Outcome Measures.** Primary and secondary registered measures are listed below.

Measure	Construct	Description	Time Frame
Family Questionnaire (FQ)	Change in Family Communication	Family communication will be assessed with the Family Questionnaire (FQ). The FQ is a 20-item self-report assessment of criticism and emotional expression in interactions with family members toward patients with mental illness. Each item is rated on a 4-point scale (1 = never/very rarely; 4 = very often). The FQ is scored by summing individual items with higher scores indicating greater levels of expressed emotion. As a primary outcome, we will examine the combined total of emotional overinvolvement and critical comments; scores range from 20 to 80 with higher scores indicating greater expressed emotion.	Baseline, 6 weeks, 12 weeks
Measure to Assess Steps to Services, Caregivers Edition (MASS-CG)	Change in Treatment Facilitation	Treatment seeking will be measured using the Measure to Assess Steps to Service-Caregivers (MASS-CG). The MASS-CG is a 23-item self-report assessment of steps taken by the caregiver towards the attainment of mental health treatment for their loved one, including research, social support, encouragement or support of the loved one's help-seeking actions, and engagement with service provider steps. Each item is endorsed on a three-point Likert scale (0 = No, I have not done this, 1 = I have done this once or twice, 2 = I have done this multiple times). The	Baseline, 6 weeks, 12 weeks

		MASS-CG is scored by summing individual items with higher scores indicating greater levels of treatment facilitation activities.	

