Brief Experience of Caregiving Inventory (BECI)	Change in Appraisal of Caregiving Experiences	Appraisals of caregiving experiences will be assessed with the Brief Experience of Caregiving Inventory (BECI). The BECI is a 19-item assessment of the impact of caregiving on the individual's life, both in negative and positive ways. The items are rated on a 5-point Likert scale (never to nearly always), and scores range from 0 to 76, with a higher score denoting more negative appraisals of one's caregiving experience.	Baseline, 6 weeks, 12 weeks
Brief COPE Inventory	Change in Caregiver Coping, Activities	Caregiver coping will be assessed with the Brief COPE Inventory, a 28-item self-	Baseline, 6 weeks, 12 weeks

		report scale of coping skills in response to stressors, based on the full COPE inventory; items generate a range of subscale scores related to specific coping areas. The instrument consists of 28 items which will be scored on a 1 to 4 Likert scale (I haven't been doing this at all to I've been doing this a lot), with higher values representing a greater frequency of engaging in each coping strategy. For this outcome, we will examine total frequency sum of items (14) assessing variables a priori selected to represent adaptive coping. Scores on this scale range from 14 to 56.	
Coping Self-Efficacy Scale (CSES)	Change in Caregiver Coping, Self-efficacy	Caregiver coping self-efficacy will be assessed with the Coping Self-Efficacy Scale, a 26-item self-report questionnaire measuring the perceived ability of coping with various life challenges. Responses are rated on a 0 to 10 scale, and scores range from 0 to 260, with higher scores denoting a greater sense of self-efficacy in coping.	Baseline, 6 weeks, 12 weeks
General Health Questionnaire, 12 Item Version (GHQ-12)	Change in Caregiver Distress	Caregiver distress (secondary mediator) will be assessed with General Health Questionnaire (GHQ), a 12-item questionnaire assessing general psychological morbidity. Respondents indicate agreement on a four-point scale (0 = Not at all; 3 = More than usual) and total scores ranging from 0 to 36 with higher scores indicating more severe psychological morbidity.	Baseline, 6 weeks, 12 weeks

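### Do 26 unadjusted between-arm tests at 0.05, with no ranked primary outcome or time point, require a multiplicity rule in this pilot?

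*Combined protocol and SAP*

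**What the plan says.** Under Outcome Measures (Methods), 13 measures appear in one table, introduced by "Primary and secondary registered measures are listed below". No column separates primary from secondary. The FQ entry reads "As a primary outcome, we will examine the combined total of emotional overinvolvement and critical comments", and the GHQ-12 entry labels distress a secondary mediator. The other entries carry no rank. The Design paragraph of the Overview uses the word more broadly, for the whole battery: "Primary outcome assessments are collected remotely with electronic data capture".

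The Data Analytic Plan covers the scales with "Linear regression will be used for continuous outcomes with treatment condition and baseline values entered as covariates" and adds "We will separately model outcomes at 6 weeks and 12 weeks respectively". The two treatment engagement reports (medication provider; therapy or counseling) get hurdle models, each with a binary part and a count part, over the 12-week follow-up. The criterion is "Models will use a two-tailed alpha level of 0.05 to detect significant differences between Bolster and control".

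Two further statements bear on the point. The sentence that sets alpha goes on to say that effect sizes and 95% intervals will be examined across all outcomes to guide later trials. The closing sentence says that, because this is a pilot, the conclusions draw on the effect sizes overall.

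**The concern.** A single 0.05 criterion applied to many comparisons, with no order among them, is a familiar route to chance findings. Even the FQ, the one measure individually called primary, is tested at two time points with neither preferred. An app with no effect could well produce at least one significant difference.

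The trial is meant to show whether a fully powered study is warranted. If the authors chose the measure and time point that happened to cross 0.05, a false signal could prompt that study. With 60 participants, the effect carried into its sample size calculation would also be too large. The significance wording also seems to pull against the statement that conclusions come from effect sizes.

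**Working it through.** The documents give no familywise error rate, power or sample size derivation, so there is no figure of theirs to reproduce. The check starts from a count of tests.

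**Inputs from the documents**
- Alpha is 0.05, two-tailed, for each Bolster versus control comparison (Data Analytic Plan).
- There are 11 continuous scales: FQ, MASS-CG, KAST, four IPQSR scores, BECI, Brief COPE, CSES and GHQ-12 (Outcome Measures).
- Each scale is tested at 2 time points.
- There are 2 engagement outcomes with 2 hurdle parts each, covering the single 12-week period.
- N = 60 allocated 2:1, so 40 and 20.

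**Count:** 11 × 2 + 2 × 2 = 22 + 4 = 26. The within-condition models are left out because the criterion is tied to Bolster versus control.

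**Expected false positives under no effect:** 26 × 0.05 = 1.3, whatever the correlation. By symmetry, half of these, 0.65, would favour the app.

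**Chance of at least one, independent tests:** 1 − 0.95^26 = 0.736.

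**Chance of at least one, correlated tests.** The documents give no correlations, so those below are assumptions. Each row is a null simulation of 200,000 multivariate-normal draws. Hurdle tests correlate 0.1 with the scales. They also correlate 0.1 with each other, except that like parts of the two hurdle models take the same-time between-scale value.

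| Same scale, two times | Different scales, same time | Different scales, different times | At least one p < 0.05 |
|---|---|---|---|
| 0.5 | 0.2 | 0.1 | 68% |
| 0.6 | 0.3 | 0.2 | 64% |
| 0.7 | 0.4 | 0.3 | 59% |
| 0.7 | 0.5 | 0.4 | 54% |
| 0.8 | 0.6 | 0.5 | 48% |
| 0.8 | 0.7 | 0.6 | 43% |

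With one common correlation among all 26 tests, the figure is 62% at 0.3, 55% at 0.4 and 48% at 0.5. So at least one false positive is more likely than not unless the tests are correlated at about 0.5 or more.

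**FQ alone, two time points:** 1 − 0.95^2 = 0.0975 if independent, and 8.7% with a correlation of 0.6.

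**What a correction would cost.** With full retention and no baseline adjustment, the standard error of a standardised difference is √(1/40 + 1/20) = 0.274.
- At 0.05, an estimate must reach about 1.96 × 0.274 = 0.54 to be significant (0.55 with the t distribution).
- Bonferroni over 26 tests, which is also Holm's first step, uses 0.05/26 = 0.0019. The normal quantile is about 3.10, so the bar is 3.10 × 0.274 = 0.85.
- Familywise error would fall to 1 − (1 − 0.05/26)^26 = 4.9%. The planned estimates and 95% intervals would not move.

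**The case for a change.** The strongest case for a change is that the effect-size statement does not withdraw the significance criterion. It says what conclusions will involve, not what they will rest on alone, so authors could stress either after seeing the data. Selection by significance would also mislead. Suppose the true effect were d = 0.2. Estimates significant in the app's favour would average about 0.68 without baseline adjustment, or about 0.55 if baseline explained 36% of the variance (an assumption), roughly three times the truth. And the wording would be cheap to alter: name FQ at 12 weeks as the one test and report the rest as estimates.

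The count and the error rates stand, as does the absence of a stated rank and time point. The inflation is also real, but it is conditional on choosing outcomes because they crossed 0.05. Nothing in the plan makes that choice, and no p-value is attached to the decision on a later trial. Since effect sizes and intervals are to be examined for all outcomes, a lone significant result will be read beside the others. A nominal alpha and an emphasis on estimation can coexist; the tension is one of emphasis.

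The proposed remedy is weaker than it looks. The FQ is described as a primary outcome, not the only one, and the table is said to mix registered primary and secondary measures. MASS-CG and the two engagement reports come next in the table with no stated rank, so a single FQ test could demote outcomes registered as primary. Nothing in the documents favours 12 weeks over 6. Holm adjustment across 26 tests in a 60-person pilot is a trade-off on which statisticians reasonably differ.

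**Conclusion.** No change is needed. The plan does run 26 unadjusted between-arm tests. With no true effect, 1.3 nominally significant results are expected, and the chance of at least one is 74% under independence or about 43% to 68% under the assumed correlations in the table. Those figures describe how to read a stray p-value. They do not show a faulty decision rule, because the plan lets no single p-value decide anything and already commits to estimates with 95% intervals throughout. Most of what a correction would be meant to achieve is therefore already planned.

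What remains is missing detail: which registered outcomes are primary, and at which time point. The report can carry over the registered designations and treat the p-values as nominal. This conclusion rests on the authors following their own closing statement about effect sizes. It would not hold if one result below 0.05 were made the ground for proceeding to a full trial or for choosing its primary outcome.
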